8.1.1.5 First Use of Ambulatory Device

The date of first use of ambulatory device will be determined through retrospective chart review, based on an EDSS score of 6.0 or higher (score of 6.0 is defined as “intermittent or unilateral constant assistance [cane, crutch, brace] required to walk about 100 meters with or without resting”) or clinical descriptions if EDSS scores are not available.

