8.1.1.6 First Use of Wheelchair

The date of first use of a wheelchair will be determined through retrospective chart review, based on an EDSS score of 7.0 or higher (score of 7.0 is defined as unable to walk beyond approximately 5 meters even with aid, essentially restricted to wheelchair; wheels self in standard wheelchair and transfers alone; up and about in wheelchair some 12 hours a day) or clinical descriptions if EDSS scores are not available.

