Time-to-event data will be calculated from first dose of IMP in the parent study and will be presented using Kaplan-Meier estimates or cumulative incidence curves as appropriate. The analytical approach will be further detailed in the SAP.

Genetic variations will be analyzed descriptively. In addition, association of genetic variations with patients experiencing long-term response will be analyzed.

Adverse events will be summarized by number and frequency of patients with events.

Endpoint	Statistical Analysis Methods
Primary	Percentage and 95% CI
Secondary	Percentage and 95% CI
Tertiary/Exploratory	Descriptive statistics and time-to-event analyses as described above

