14.3.2 Durability of clinical outcomes

Durability of clinical outcomes will be summarized descriptively and evaluated via retrospective data collection from medical records or at Study Visit 1:

- Proportion of study participants being bedridden
- Time from first dose of IMP to first use of an ambulatory device
- Time from last dose of IMP to first use of an ambulatory device
- Time from first dose of IMP to first use of a wheelchair
- Time from last dose of IMP to first use of a wheelchair
- Number of MS relapses between the end of parent study to Study Visit 1
- ARR from time of first dose of IMP to SV1, and by 2-year intervals
- ARR from time of last dose of IMP to SV1, and by 2-year intervals
- % and Time to conversion to CDMS (For Cohort D participants only)
- Proportion of study participants diagnosed as Secondary Progressive MS (SPMS) without relapses in the 3 months prior to SPMS diagnosis
- Proportion of study participants diagnosed as SPMS with relapses in the 3 months prior to SPMS diagnosis
- Proportion of study participants diagnosed as Primary Progressive MS (PPMS) (For Cohort D participants only)

Computational rule:

Participants being bedridden, first use of an ambulatory device and first use of a wheelchair are collected on “ambulatory - bedridden status and first use of wheelchair” eCRF page.

Participants diagnosed as SPMS with and without relapses in the 3 months prior to SPMS diagnosis are collected on “History of MS onset” eCRF page and Participants diagnosed as PPMS are collected on “conversion to CDMS” eCRF page.

Time to first ambulatory device/wheelchair

Kaplan Meier curve and estimates including number of subjects at risk, number of subjects with an event and subject censored will be presented for time to first ambulatory and wheelchair from first and last dose of IMP administered, by treatment group (exposed vs never exposed) and overall

Computation rule:

Whichever come first will be considered as an event:

- 1) CRF Ambulatory device page, wheelchair use date
- 2) CRF Ambulatory device page, ambulatory device use date
- 3) EDSS score ≥ 6
- 4) Death due to MS

Kaplan Meier SAS code:

AVAL = time-to-event response variable

CENSOR = censoring variable (0 = event, 1 = no event)

TRT= Trt group (“Exposed to Clad” “Never exposed to Clad”)

Code:

```
PROC LIFETEST DATA=ADTTE OUTSURV=RESULTS ALPHA=0.05 METHOD= KM Conftype =  
Loglog;  
TIME AVAL*CENSOR(1);  
STRATA TRT;  
RUN;
```

Annualized Relapse Rate:

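### SAP 14.3.2 has no wheelchair-specific Kaplan-Meier event rule; its single rule gives time to first walking device or worse

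*SAP*

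**What the plan says.** Protocol section 3 lists time to first ambulatory device and time to first wheelchair as two tertiary endpoints, and sections 8.1.1.5 and 8.1.1.6 give them different thresholds. For the device: "The date of first use of ambulatory device will be determined through retrospective chart review, based on an EDSS score of 6.0 or higher". For the wheelchair: "The date of first use of a wheelchair will be determined through retrospective chart review, based on an EDSS score of 7.0 or higher". In both cases a clinical description may stand in when no EDSS score is available. On analysis, protocol 9.4 says "Time-to-event data will be calculated from first dose of IMP in the parent study", with results "presented using Kaplan-Meier estimates or cumulative incidence curves as appropriate". Its closing methods table assigns time-to-event analyses as well as descriptive statistics to the tertiary endpoints.

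SAP 14.3.2 keeps the endpoints apart in its list, where one item is "Time from first dose of IMP to first use of a wheelchair", and adds versions timed from last dose. It then announces Kaplan-Meier curves and estimates for "time to first ambulatory and wheelchair from first and last dose of IMP administered" under a combined device/wheelchair subheading. One computation rule follows: "Whichever come first will be considered as an event", applied to four items, namely the wheelchair date, the device date, an EDSS of 6 or more, and death from MS. In SAP 17.1 the Kaplan-Meier outputs are Table 15.2.6.2 and Figures 15.2.6.1 and 15.2.6.2, all with combined device/wheelchair titles. SAP 7 states that nothing differs from the protocol's planned analyses.

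**The concern.** The protocol treats needing a walking aid and being essentially confined to a wheelchair as different milestones. Appendix 5 describes patients at EDSS 6.0 and 6.5 as still walking, with one-sided or two-sided support. A rule that fires at the first of these milestones answers the device question. It cannot also answer the wheelchair question, because every device user has already had an event.

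At stake is one tertiary result. A programmer following the SAP would produce a device-or-worse curve and no wheelchair curve. A reader of the report could take the combined curve as information about wheelchair use, which it would overstate in frequency and place too early. With no change declared in SAP 7, nothing would alert that reader to the merge.

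**Working it through.** No figure in the plan applies here, so the check compares the two rules on the same patient histories.

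Notation, as times from first dose: W = wheelchair date, D = device date, E6 = first EDSS of 6.0 or higher, E7 = first EDSS of 7.0 or higher, M = death from MS.

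- Rule in SAP 14.3.2: T_SAP = min(W, D, E6, M).
- Rule implied by protocol 8.1.1.6: T_wheelchair = min(W, E7).

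Any score of 7.0 or higher is also 6.0 or higher, so E6 ≤ E7. Both minima contain W. Hence T_SAP ≤ T_wheelchair for every patient. The inequality is strict whenever a device, or EDSS 6.0 or 6.5, is recorded first.

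| History (years from first dose) | SAP 14.3.2 rule | Wheelchair date or first EDSS 7.0 or higher |
|---|---|---|
| Cane and EDSS 6 at 4, never a wheelchair | Event at 4 | Censored |
| EDSS 6.0 at 5, nothing further | Event at 5 | Censored |
| Cane and EDSS 6 at 4, wheelchair and EDSS 7 at 9 | Event at 4 | Event at 9 (9 − 4 = 5 years later) |
| MS death at 8, no device or EDSS record | Event at 8 | Event at 8 if MS death counts; otherwise censored |
| No milestone | Censored | Censored |

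The first two rows show added events. The third shows an event of the right kind of patient at the wrong time. The fourth shows a choice that a wheelchair rule would have to state.

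Could the wheelchair curve be obtained by applying only part of the SAP rule? Keeping the EDSS item still counts scores of 6.0 and 6.5. Dropping it and using the wheelchair date alone misses a patient whose only evidence is a charted EDSS of 7.0 or higher, which protocol 8.1.1.6 accepts. No subset of the four items reproduces the protocol definition.

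Size: if a share w reaches the wheelchair milestone and a further share d reaches only a device or EDSS 6.0–6.5, the ratio of event counts (leaving MS death aside) is (w + d)/w = 1 + d/w. Protocol 9.2 offers planning values of 5%, 10% and 15% for w. Neither document gives d, so the ratio cannot be computed.

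**The case against.** The best defence is that one composite was intended and is openly labelled. The subheading, the single rule and all three output titles combine device and wheelchair. Wheelchair-only times stay in the list of items to be summarized descriptively, have their own eCRF item, and could appear in Table 15.2.6.1. Protocol 9.4 itself says tertiary endpoints collected retrospectively or at Study Visit 1 are analyzed descriptively.

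Much of this stands. The composite reading is plausible, and the labelling is not misleading about what is combined. But that reading leaves the protocol's separate endpoint without the time-to-event presentation that protocol 9.4 also plans, and SAP 7 would then need to say so. No event or censoring rule is given for a wheelchair line in Table 15.2.6.1.

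A reader might infer more than the documents support:

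- That the wheelchair endpoint is lost. It is not: the data are collected and the times remain listed.
- That EDSS events during the parent studies are missed, because chart-abstracted EDSS starts at the end of the parent study. SAP 6.3 brings in the parent-study datasets; the rule merely does not name its EDSS source.
- That non-MS death is ignored. The SAP's coding has only event and no event, and only MS death is an event, so a non-MS death with no earlier milestone is implicitly censored. What is unstated is the censoring date.

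**Conclusion.** The point holds as a specification error in one tertiary analysis. The only Kaplan-Meier rule in SAP 14.3.2 suits the ambulatory-device endpoint and gives the wrong result for the wheelchair endpoint, which is left without a Kaplan-Meier or cumulative incidence result.

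The direction is certain: the rule can only add events and bring them forward relative to a wheelchair rule. The amount is unknown, since it depends on how many patients reach a device or EDSS 6.0–6.5 and go no further, or do so well before a wheelchair. It would be tempting to attach a multiplier, but that would rest on an assumed share found nowhere in the documents.

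Nor does the point reach the primary endpoint, which has its own EDSS 7 rule and named sources in SAP 14.1. The study is exploratory with no formal hypothesis. The conclusion rests on the rule being applied as written and on output titles alone, because table shells are not among the documents.

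**What to change.** 1. Keep the current rule, labelled as the device endpoint or as a device/wheelchair composite, with MS death stated as a component.
2. Add a wheelchair rule: the earlier of the wheelchair use date and the first EDSS of 7.0 or higher. Bedridden status (EDSS 8.0 or higher in protocol 8.1.1.3) and MS death (EDSS 10.0 in Appendix 5) meet that threshold; state whether they count when known without an EDSS score.
3. Add a matching Kaplan-Meier or cumulative incidence table and figures from first dose, by exposure group and overall.
4. If only the composite is wanted, declare this in SAP 7 instead of steps 2 and 3.

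Naming the EDSS sources and the censoring date, including for deceased or lost patients without a Study Visit 1, would be a useful but optional clarification.

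The cost is SAP wording, one further derived time-to-event variable, and about one table and two figures modelled on Table 15.2.6.2 and Figures 15.2.6.1 and 15.2.6.2. No new data are needed: wheelchair, device and bedridden information is on the ambulatory eCRF page, and EDSS comes from the retrospective page, Study Visit 1 and the parent-study datasets.

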4.0 Able to walk at least 500 meters without aid

4.5 Able to walk 300-499 meters without aid

5.0 Able to walk 200-299 meters without aid

5.5 Able to walk 100-199 meters without aid

6.0 Able to walk 5-99 meters without aid or with unilateral assistance is able to walk at least 100 meters

6.5 Bilateral assistance required to walk but able to walk at least 20 meters; or unilateral assistance needed but able to walk between 5-99 meters

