7.0 Only able to walk between 1- 5 meters even with assistance

7.5 Unable to walk more than a few steps (i.e., not able to walk at all or able to walk a maximum of about 1 meter)

8.0-9.5 Investigator judgment

The guiding principle: if a patient fails to meet the criteria of a given level, they are automatically assigned to the next higher level. If a patient does not need aids to walk (i.e., walks unassisted) but can only walk 50 meters, they are to be considered EDSS 6.0 since they do not satisfy the criteria for EDSS 5.5.

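### An EDSS score of 6.0 is counted as first ambulatory device use, although Appendix 5 also gives 6.0 to patients who walk 5 to 99 m without any aid (minor)

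*SAP*

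**What the plan says.** The tertiary endpoint in SAP 14.3.2 is "Time from first dose of IMP to first use of an ambulatory device", with a parallel version counted from the last dose. The event date is the earliest of four items: the wheelchair date and the device date from the eCRF, an EDSS of 6 or more, and death due to MS. The instruction is "Whichever come first will be considered as an event". The same section says that bedridden status, "first use of an ambulatory device and first use of a wheelchair are collected on" a dedicated eCRF page.

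The EDSS component comes from the protocol. Section 8.1.1.5 states: "The date of first use of ambulatory device will be determined through retrospective chart review, based on an EDSS score of 6.0 or higher". It goes on to describe 6.0 as the level at which a cane, crutch or brace is needed, and it allows clinical descriptions where no EDSS is available. Section 8.1.1.1 makes the same assumption about a score of 6.

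Protocol Appendix 5 has two entries for 6.0. The descriptive scale requires assistance. The list of walking distances, which the appendix says determines scores from 4.5 upward, defines 6.0 as "Able to walk 5-99 meters without aid or with unilateral assistance is able to walk at least 100 meters". The guiding principle then gives an example: patients who need no walking aid but "can only walk 50 meters, they are to be considered EDSS 6.0".

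**The concern.** The endpoint is named as use of a device. The rule rests on the premise that a score of 6.0 implies such use, and the study's own scoring instructions do not support that premise. A patient who walks a short distance unaided and scores 6.0 enters the curve as a device user on that date. SAP 14.3.2 neither sets such scores aside nor checks them against the recorded device date.

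Table 15.2.6.2 and Figures 15.2.6.1 and 15.2.6.2 present the result as time to first device or wheelchair, and their titles do not mention EDSS. All three are flagged for the interim analysis, whose results SAP 6.4 says have been disseminated. A reader would take the curves as evidence about device use when part of what they show may be walking distance.

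**Working it through.** The documents give no event count, rate or sample size for this endpoint, so there is no planned figure to reproduce. The check has three parts.

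**1. Which scores can arise without an aid.** From the distance list in Appendix 5:

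| Score | Distance rule, paraphrased | Unaided route? |
|---|---|---|
| 5.5 | 100 to 199 m unaided | below the threshold |
| 6.0 | 5 to 99 m unaided, or at least 100 m with one-sided aid | yes |
| 6.5 | two-sided aid for at least 20 m, or one-sided aid for 5 to 99 m | no |
| 7.0 | 1 to 5 m even with assistance | no |

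Scores above 7.0 describe patients who cannot walk more than a few steps. Only a score of exactly 6.0 is affected.

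**2. Direction.** Let W be the wheelchair date, D the device date, E the date of the first EDSS of 6 or more, and M the date of MS death.

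- SAP rule: T = min(W, D, E, M).
- Rule without the EDSS component: T' = min(W, D, M).
- Always T ≤ T', so the EDSS component can only add events or bring them forward relative to recorded dates and MS death.

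Two hypothetical patients:

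- Unaided over 60 m, scored 6.0 at year 5, first cane at year 8. The rule gives year 5, which is 8 − 5 = 3 years early.
- Unaided over 80 m, scored 6.0 at Study Visit 1, never uses a device. The rule gives an event where there is none.

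A third patient limits this result. Real device use with no recorded date is missed by T'. The rule recovers it at E, which may fall later than the true first use. The net error of the whole curve against true use therefore has no fixed sign.

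**3. Size of the unaided-6.0 error, on assumed inputs.** None of these inputs is in the documents:

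- ten-year incidence p of a first EDSS of 6 or more: 15% or 30%, with exponential times;
- share u of those first scores that are unaided 6.0: 5% to 30%;
- delay from that score to real device use: exponential with mean 1 or 3 years, or never.

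The true ten-year device proportion is (1 − u)·p + u·G(10), where G is the distribution function of the time to the score plus the delay. If the patient never uses a device, G = 0.

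| p | u | Delay | Rule at 10 y | True use at 10 y | Excess (points) |
|---|---|---|---|---|---|
| 15% | 5% | mean 1 y | 15.0% | 14.9% | 0.1 |
| 15% | 30% | mean 3 y | 15.0% | 13.8% | 1.2 |
| 15% | 30% | never | 15.0% | 0.70 × 15.0 = 10.5% | 4.5 |
| 30% | 5% | mean 1 y | 30.0% | 29.9% | 0.1 |
| 30% | 30% | mean 3 y | 30.0% | 27.6% | 2.4 |
| 30% | 30% | never | 30.0% | 0.70 × 30.0 = 21.0% | 9.0 |

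The time by which 10% have an event moves from about 6.5 years under the rule to between 6.5 and 9.5 years when p = 15%. When p = 30% it moves from about 3.0 years to between 3.0 and 4.3 years. A simulation of two million patients agrees with these values to within rounding and sampling error. With u = 0 the excess is zero.

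**The case against.** The strongest reply is that the SAP invents nothing. Protocol 8.1.1.5 makes EDSS the first source and clinical description the fallback, and the endpoint tables carry a footnote allowing mobility endpoints to be determined from EDSS. SAP 14.3.2 states the composite rule openly, and including MS death makes it visibly broader than device use. The rule is the same for both exposure groups, no hypothesis is tested, and EDSS of 6.0 or higher is already reported under its own name in SAP 14.2.1. All of this is correct, and it lowers the severity. It does not remove the conflict, which then also lies inside the protocol, between 8.1.1.1 and 8.1.1.5 on one side and the Appendix 5 distance rule on the other.

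A reader might infer three stronger conclusions that the documents do not support.

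- *The whole Kaplan-Meier curve is too early.* EDSS can also pick up undated device use, possibly late, so the net bias is not fixed.
- *The eCRF page holds the true answer and should override EDSS.* The page is not in the documents, and nothing shows that it offers a no-device response. Under 8.1.1.5 its date may itself come from a 6.0 score. Full priority for the page would also discard scores of 6.5 or higher, which have no unaided route.
- *The error is known to be material.* Neither the unaided share nor the delay is given. Retrospective scores come from medical records, and the documents do not say that these were scored with the Appendix 5 distances.

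**Conclusion.** The point holds in a limited form. Under the earliest-of rule, every patient scored 6.0 while walking 5 to 99 m unaided is counted as a device or wheelchair event at that score, unless another component came first. For those patients the event is early or false. Their number is unknown and may be zero. Under the assumed ranges the excess at ten years runs from about 0.1 to 9 percentage points, and the upper end needs 30% incidence, a 30% unaided share and no later device use. What follows for the outputs is that they describe a composite milestone and cannot be read as device use alone. Severity is minor: the endpoint is tertiary and descriptive, and the primary endpoint does not use the 6.0 threshold.

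**What to change.** 1. Retitle Table 15.2.6.2 and Figures 15.2.6.1 and 15.2.6.2 as time to the composite of device or wheelchair use, EDSS of 6.0 or higher, or MS death.
2. Add to SAP 14.3.2 one Kaplan-Meier analysis of device or wheelchair use. Its events are a recorded device or wheelchair date, an EDSS of 6.5 or higher, or MS death, whichever is earliest. A score of exactly 6.0 counts only if device use is documented.
3. Reconcile protocol 8.1.1.1 and 8.1.1.5 with Appendix 5, so that the recorded first-use date means documented use and is not taken from a 6.0 score alone. Without this step, the recorded dates in the added analysis could carry the same problem.

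The cost is one extra derivation and output, new titles, and a protocol clarification. The added curve will have no more events than the present one and probably fewer. It may also miss real device use at 6.0 where the chart is silent, so the two curves should be shown together.

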The second visit is Study Visit 1, which could be combined with the Screening Visit. At this visit retrospective data (from medical chart review) and current data will be collected. For patients who are able to attend the visit at the clinic data on a physical assessment, Expanded Disability Status Scale (EDSS), Patient-Reported Outcomes (PROs), cognitive assessments, AEs and concomitant medications will be collected. For all patients the following retrospective data will be collected: EDSS, Secondary Progressive MS (SPMS) conversion, details of subsequent DMDs, including physician questions on treatment decisions, date of first use of an ambulatory device or wheelchair, date of first time bedridden and relapse history from end of parent study to Study Visit 1. In ORACLE MS patients, CDMS conversion and PPMS diagnosis will be assessed as well. An optional blood sample for pharmacogenetic testing will be taken from patients who consent to the optional sampling at the clinic and who are seen at a site with available capabilities to store and ship these samples. Patients will also have the opportunity to provide pharmacogenetic samples after Study Visit 1 and up to 6 months from Screening (unless last patient enrolment has occurred, in which case the sample can only be collected at Study Visit 1).

For patients from whom in-person EDSS at clinic visit was not planned to be collected, a telephone EDSS questionnaire will be administered. Attempts should be made to administer the telephone EDSS within 14 days after informed consent was received for patients not attending the clinic visit.

Study data will be supplemented with information from the past clinical trial(s), which will be integrated for milestones such as interim analyses and, if needed, on a regular basis. It is the Sponsor, not the site, that is responsible for obtaining the information from the past clinical trial(s) study databases. However, the sites will be requested to provide some patient identifiers (e.g. patient number, parent study patient participated in, year of birth and gender) to match data being collected with previous data sets.

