8.1.1.7 Relapse Count

The following information on relapses will be recorded on the relapse module of the eCRF, if available: the number of relapses from end of parent study to Study Visit 1; relapse onset date and stabilization/resolution date; estimated relapse duration; maximal EDSS at time of relapse (if known); major systems affected; treatment required for relapse; patient hospitalization for relapse; outcome of relapse (i.e. increase in disability). A relapse will be defined as patient-reported symptoms and objectively observed signs typical of an acute inflammatory demyelinating event in the CNS, developing acutely or sub-acutely, with duration of at least 24 hours, in the absence of fever or infection (Thompson, 2018).

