6.2 Summary of Parent Studies

CLARITY (25643): The CLARITY (CLAdRibine Tablets treating MS orally) study was a multicenter, randomized, double-blind, three treatment group study of 96 weeks duration. Depending on their body weight, subjects took 1 or 2 cladribine 10 mg tablets (or matching placebo) per day over 4 to 5 days in either (a) Week 1 and Week 5 of Years 1 and 2, or (b) in Weeks 1, 5, 9, and 13 of Year 1, followed by Weeks 1 and 5 of Year 2, for a cumulative dose of 3.5 and 5.25 mg/kg, respectively. The primary objective of the trial was to evaluate the efficacy of cladribine versus placebo in the reduction of qualifying relapse rate during 96 weeks of treatment in subjects with RRMS. The secondary objectives were to assess the effect of cladribine on progression of disability (EDSS) and lesion activity as measured by MRI.

CLARITY EXT (27820): The CLARITY EXT (CLAdRibine Tablets treating MS orally EXTension) study was a randomized, double-blind, 96-week Extension study to evaluate the long-term safety and efficacy of oral cladribine in subjects with RRMS who had completed the CLARITY study. In the CLARITY EXT study, only the lower dose of cladribine was administered (subjects took 1 or 2 cladribine 10 mg tablets (or matching placebo) per day over 4 to 5 days in Week 1 and Week 5 of Years 1 and 2, for a cumulative dose of 3.5 mg/kg). Subjects who were assigned to the placebo arm in CLARITY were assigned to cladribine treatment. Subjects who received cladribine in CLARITY were randomized to either placebo or cladribine 3.5 mg/kg treatment groups in a 1:2 ratio, creating 5 arms:

Cladribine high/low dose (HLLL): Subjects who were randomized to cladribine high dose with 1 or 2 cladribine 10 mg tablets per day over 4 to 5 days in Weeks 1, 5, 9, and 13 of Year 1, followed by Weeks 1 and 5 of Year 2 of the CLARITY study (25643) (total dose 5.25 mg/kg), and to cladribine low dose with 1 or 2 cladribine 10 mg tablets per day over 4 to 5 days in Week 1 and Week 5 of Years 1 and 2 of the CLARITY extension study (total dose 3.5 mg/kg).

Cladribine low/low dose (LLLL): Subjects who were randomized to cladribine low dose with 1 or 2 cladribine 10 mg tablets per day over 4 to 5 days in Week 1 and Week 5 of Years 1 and 2 of the CLARITY study (25643) (total dose 3.5 mg/kg), then to cladribine low dose with 1 or 2 cladribine 10 mg tablets per day over 4 to 5 days in Week 1 and Week 5 of Years 1 and 2 of the CLARITY extension study (total dose 3.5 mg/kg).

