Cladribine high/placebo (HLPP): Subjects who were randomized to cladribine high dose with 1 or 2 cladribine 10 mg tablets per day over 4 to 5 days in Weeks 1, 5, 9, and 13 of Year 1, followed by Weeks 1 and 5 of Year 2 of the CLARITY study (25643) (total dose 5.25 mg/kg), and then to placebo for the years 1 and 2 of the CLARITY extension.

Cladribine low/placebo (LLPP): Subjects who were randomized to cladribine low dose with 1 or 2 cladribine 10 mg tablets per day over 4 to 5 days in Week 1 and Week 5 of Years 1 and 2 of the CLARITY study (25643) (total dose 3.5 mg/kg), then on placebo for the years 1 and 2 of the CLARITY extension study.

Placebo/Cladribine low dose (PPLL): Subjects who were randomized to placebo for the first and second year of CLARITY study (25643), then to cladribine low dose with 1 or 2 cladribine 10 mg tablets per day over 4 to 5 days in Week 1 and Week 5 of Years 1 and 2 of the CLARITY extension study.

Due to administrative reasons, there was a varying period (median time 41 weeks, range 1 day to 118 weeks) between a subject completing the CLARITY study and starting in the CLARITY EXT study, subjects did not receive cladribine during this time period. Following the end of the 96-week CLARITY EXT study period, subjects were followed for safety for an additional 24 weeks. The primary objective of this trial was to evaluate the safety of extended treatment with oral cladribine when administered to subjects who completed CLARITY (25643).

ORACLE MS (28821): The ORACLE MS (ORAl CLadribine in Early MS) study was a Phase III, randomized, double-blind study to evaluate the safety and efficacy of oral cladribine tablets as a monotherapy in subjects at risk of developing MS (subjects who have experienced a first clinical event suggestive of MS). Subjects were randomized to either oral cladribine high dose with 1 or 2 cladribine 10 mg tablets per day over 4 to 5 days in Weeks 1, 5, 9, and 13 of Year 1, followed by Weeks 1 and 5 of Year 2 (total dose 5.25 mg/kg), or oral cladribine low dose with 1 or 2 cladribine 10 mg tablets per day over 4 to 5 days in Week 1 and Week 5 of Years 1 and 2 (total dose 3.5 mg/kg), or matching placebo. The design was a time-to event design with treatment schedules dependent on conversion to clinically definite multiple sclerosis (CDMS) according to the Poser criteria at any time during the first 96 weeks:

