9.3 Timepoints

- **Date of First dose of IMP (FDIMP)** is the day of start of first study drug intervention (placebo or cladribine).
- **Date of Last dose of IMP (LDIMP)** is the day of end of study drug intervention (placebo or cladribine). For ORACLE patient both ITP and open label period will be observed to identify the end of study drug intervention.
- **The end of the parent study** is defined as the last date of data collection from the parent study.

- **Baseline** (of parent study) is defined as PSD1 baseline, which is the last assessment prior to or at FDIMP.

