ARR from time of FDIMP to Study Visit 1 is calculated for each treatment group:

$$\text{ARR} = [(\text{sum of relapses} * 365.25) / (\text{sum of time on study in days until SV1})]$$

ARR from time of FDIMP to Study Visit 1 and by 2-year intervals is calculated for each treatment group:

$ARR = [(sum\ of\ relapses\ *365.25) / (sum\ of\ time\ on\ main\ study\ by\ 2\text{-}year\ intervals\ in\ days\ until\ SV1)]$

Time on study = Study Visit 1 – first dose of IMP +1

ARR from time of last dose of IMP to Study Visit 1 will be calculated similarly.

Table 5: Time window for ARR by 2-year intervals

Cumulative intervals	Time intervals
Less than 2 years	1 to 730 days
2 nd years to 4 th years	731 to 1461 days
4 th years to 6 th years	1462 to 2191 days
6 th years to 8 th years	2192 to 2922 days
X th years to Y th years...	Truncate (X*365.25 +1) to truncate (Y*365.25) days

Time to CDMS (Cohort D only)

Number of participants who converted to CDMS since first and last dose administered will be summarized descriptively.

Both information collected in “Conversion to CDMS” eCRF page and ORACLE MS parent study dataset will be used to identify participants who converted to CDMS after first/last dose of IMP.

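### ARR from first dose counts the CLARITY to CLARITY-EXT gap as person-time, but neither document shows that relapses in that gap are counted

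*SAP*

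**What the plan says.** SAP 14.3.2 defines ARR from first dose as relapses × 365.25 divided by "sum of time on study in days until SV1", with "Time on study = Study Visit 1 – first dose of IMP +1". It repeats the calculation by 2-year interval, using the day windows of Table 5. The interval denominator speaks of time on the main study, a term the SAP does not define. No period is deducted in either formula.

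SAP 6.2 reports a "varying period (median time 41 weeks, range 1 day to 118 weeks) between a subject completing the CLARITY study" and starting the extension. It says that no cladribine was given in that time. It does not say whether relapses were recorded.

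Two sources of relapses are described:
- **After the parent study:** the relapse module of the CLASSIC-MS eCRF records "the number of relapses from end of parent study to Study Visit 1" (Protocol 8.1.1.7). Under SAP 9.3 the end of the parent study "is defined as the last date of data collection from the parent study".
- **Before that:** the parent-study databases (Protocol 4.1, SAP 6.3).

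On grouping, SAP 8.2.1 counts any patient with at least one dose of cladribine as exposed, including those who switched from placebo in the extension. SAP 6.2 states that "Subjects who were assigned to the placebo arm in CLARITY were assigned to cladribine treatment", and each of its five extension arms includes cladribine. SAP 8.2.2 and Protocol 9.3 nonetheless list participants who had placebo in both trials. SAP 14 runs analyses by exposure group for Cohort A unless otherwise specified, and the one durability table listed in SAP 17.1 (Table 15.2.6.1) is for Cohort A.

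**The concern.** A rate is sound only if its numerator and denominator cover the same time. Here the denominator includes the gap between the trials, and no stated source is shown to supply relapses for it. If none does, those days add person-time without events and pull ARR down.

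The effect would be uneven. Only patients who entered CLARITY-EXT have such a gap, and by the arms in SAP 6.2 they all fall in the exposed group. The exposed ARR, shown beside the never-exposed ARR, would look lower for a reason unrelated to treatment. The gap also falls mostly in the 2-4 year window, just after CLARITY, so an artificial dip there could be taken for durability of effect, which is what the interval analysis is meant to describe.

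**Working it through.** **Inputs from the documents**
- CLARITY duration: 96 weeks (SAP 6.2).
- Gap: median 41 weeks, maximum 118 weeks (SAP 6.2).
- Patients: 1326 in CLARITY, of whom 867 entered CLARITY-EXT; 617 in ORACLE MS (SAP 6.1).
- Follow-up: around 10 years from initial treatment (Protocol 9). I use 10 to 15 years as an assumed range.

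**The plan's own windows.** Truncating X × 365.25 + 1 and Y × 365.25 gives 1-730, 731-1461, 1462-2191 and 2192-2922 days, which matches Table 5.

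**Position of the gap**
- CLARITY: 96 × 7 = 672 days, so the gap starts at about day 673.
- Median gap: 41 × 7 = 287 days, that is days 673-959.
- Maximum gap: 118 × 7 = 826 days, that is days 673-1498.

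**Formula.** If gap relapses are uncounted and the relapse rate is constant, the estimated rate is the true rate × (T − g)/T, where T is person-time and g is gap time. The relative understatement is g/T for one patient and s × g/T for a group in which a share s entered the extension.

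**Per extension patient**

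| Period | Median gap | Maximum gap |
|---|---|---|
| Days 1-730 | 58/730 = 7.9% | 58/730 = 7.9% |
| Days 731-1461 | 229/731 = 31.3% | 731/731 = 100% |
| Days 1462-2191 | 0 | 37/730 = 5.1% |
| First dose to SV1, 10 years | 287/3652.5 = 7.9% | 826/3652.5 = 22.6% |
| First dose to SV1, 15 years | 287/5478.75 = 5.2% | 826/5478.75 = 15.1% |

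**Share of extension entrants in the Cohort A exposed group.** The documents do not give it. I assume CLARITY arms of equal size, extension entrants in equal thirds by CLARITY arm, between two thirds (411) and all (617) of the ORACLE MS patients exposed, and equal uptake into CLASSIC-MS.
- CLARITY cladribine patients: 1326 × 2/3 = 884.
- Placebo patients who switched: 867/3 = 289.
- Exposed from CLARITY and CLARITY-EXT: 884 + 289 = 1173.
- With ORACLE MS: 1173 + 411 = 1584 to 1173 + 617 = 1790.
- Share: 867/1584 = 55% to 867/1790 = 48%.

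**Cohort A exposed group, median gap**
- Years 2-4: 0.48 × 31.3% = 15.0% to 0.55 × 31.3% = 17.2%.
- Overall, 10 years: 0.48 × 7.9% = 3.8% to 0.55 × 7.9% = 4.3%.
- Overall, 15 years: 0.48 × 5.2% = 2.5% to 0.55 × 5.2% = 2.9%.

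The median stands in for the mean gap, which is not given.

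**The case against.** The strongest reply is that no passage says gap relapses are missing. SAP 6.2 describes a break in dosing, not in data. If CLARITY-EXT recorded relapses since CLARITY, for instance at entry, the numerator is complete and nothing is understated. This stands. A reader might infer that ARR is certainly biased downward; the documents support only the conditional statement.

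Further points against:
- **End of the parent study.** SAP 9.3 does not say which trial it means for extension patients. The end of CLARITY-EXT is the natural reading: the responder rules in SAP 8.2.2 use parent data from last dose to that date, and the end of CLARITY would precede last dose for patients dosed in the extension. It remains an inference.
- **Exposed patients only.** A reader might infer this from the five arms. The placebo-in-both-trials category would be never exposed and would have a gap, so the claim cannot be absolute.
- **A larger pooled figure.** A reader might take 867/1326 = 65% and obtain 0.654 × 31.3%, about 20%, for years 2-4. That is all of Cohort B with both exposure groups combined. No such ARR table is listed.
- **A companion analysis.** The SAP also plans ARR from last dose. Last dose counts cladribine or placebo (SAP 9.3), so for patients dosed in CLARITY-EXT it falls after the gap and that ARR is unaffected. This limits the damage but leaves the first-dose ARR, the version named as a protocol endpoint, as it is.
- **Low stakes.** ARR is a tertiary, descriptive endpoint with no hypothesis test. That bears on priority, not on whether the rate is correctly defined.
- **One-sided subtraction.** Removing gap days while keeping any recorded gap relapses would inflate ARR. This is right, and the fix must treat numerator and denominator together.

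**Conclusion.** The point holds as a conditional one. SAP 14.3.2 places the gap in the denominator, and the documents do not establish that the numerator covers it. If the parent data lack gap relapses, the understatement is modest overall but material in the 2-4 year window, and by design it falls almost entirely on the exposed group. The per-patient figures (31% of years 2-4, 8% of the first window, about 5-8% overall) rest on the median gap, CLARITY lasting exactly 96 weeks from first dose, and a constant relapse rate. The Cohort A figures (roughly 15-17% in years 2-4, 2.5-4.3% overall) also rest on the assumed 48-55% share of extension entrants. The change is worth making before the final analysis because it corrects a stated computation rule cheaply. The durability table is not marked for the interim analysis, so there is no listed interim version of it to revise.

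**What to change.** In SAP 14.3.2, for ARR from first dose, overall and by 2-year interval:
1. Exclude from person-time the days between the last CLARITY data date and the first CLARITY-EXT data date.
2. Exclude from the numerator any relapse with onset in those days. Done together, these give a rate for observed time whether or not gap relapses were recorded.
3. If the CLARITY-EXT datasets are confirmed to capture gap relapses fully, name that source in the SAP and keep both the days and the relapses.
4. Define the interval denominator's undefined term in the same way as time on study, with the same treatment of the gap.
5. State in SAP 9.3 which trial sets the end of the parent study for extension patients, and reconcile the placebo-in-both-trials category in SAP 8.2.2 and Protocol 9.3 with the five arms in SAP 6.2.

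The cost is a few sentences in the SAP, one date derivation from data the sponsor already holds, and slightly less person-time. No new data collection is needed.
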